For the analysis of the intervention effect over time, we will conduct a modified stepped-wedge analysis. This analysis takes into account the hierarchical nature of the data, with episodes of care occurring over time, and being nested within DWHPs. In the stepped wedge analysis, calendar time is divided into steps, corresponding to the time periods when providers are initially exposed to the intervention.

Sample Size and Power Calculations: The power calculations are predicated on the goal of evaluating the performance of DWHPs through the episodes of care they see. There are two levels of clustering: DWHPs within healthcare systems and episodes of care within DWHPs. We are making the assumption that there is little or no correlation between the DWHPs. As a result, we performed the calculations via the single level of clustering within DWHPs, with the episode of care as the unit of analysis. We will assume two values for the intra-cluster correlation coefficient (ICC): 0.03 and 0.05. The latter is relatively large compared to results that have been reported in the literature. The calculations assume a two-tailed 5% significance level and power of 80% to detect a difference between the study arms (with the study arm referring to intervention versus control, and including all data collection in each of those study periods, respectively). The statistical test involved is a simple z-test for the comparison of two proportions, but the actual analysis will be more sophisticated using covariates and adjusting for the actual number of episodes seen by a given DWHP. Thus, it can be assumed that the sample size calculations presented here are conservative.

With a baseline estimate from our preliminary data that 67% of episodes of care are fully proficient, then with 25 episodes of care per DWHP, we could detect small to medium effects of the intervention (see Table 2). If the baseline proficiency was 80%, then we could detect a medium size intervention effect, whereas if the baseline proficiency was 50%, we could detect a very small effect. If we increased the number of eligible episodes of care from which to measure proficiency to 50 per DWHP, then with a baseline proficiency of 67%, we could detect a small intervention effect. The number of available DWHPs (approximately 20 per study arm) and episodes of care provides us with >80% power.

Table 2: Number of DWHPs needed to detect the effects in each scenario with 80% power

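### Adjusting for the actual number of episodes per provider does not make Table 2 conservative: the table already assumes equal counts, the best case for a given mean

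*Combined protocol and SAP*

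**What the plan says.** The Sample Size and Power Calculations section (Aim #1) sizes the study on episodes of care clustered within DWHPs. It describes the method in these terms: "The statistical test involved is a simple z-test for the comparison of two proportions", and "we performed the calculations via the single level of clustering within DWHPs". The values used are "intra-cluster correlation coefficient (ICC): 0.03 and 0.05", with 25 or 50 episodes per DWHP per arm, a two-sided 5% level and 80% power.

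The section then says that the real analysis will go further, by using covariates and by "adjusting for the actual number of episodes seen by a given DWHP". From these two grounds it concludes: "Thus, it can be assumed that the sample size calculations presented here are conservative". The next paragraph closes with the claim: "The number of available DWHPs (approximately 20 per study arm) and episodes of care provides us with >80% power".

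The section states no CV of episode counts, no minimum or quota per DWHP, and no allowance for unequal cluster sizes.

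**The concern.** A calculation is conservative if the real study should have at least the stated power. One of the two grounds offered for this is that the analysis will deal with differing episode counts. But differing counts are a source of lost precision, and Table 2 makes no allowance for them. Adjusting for them limits that loss; it does not create a margin.

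The documents also give reason to expect counts to differ. The Dependent Variables text draws on records of all female patients seen by DWHPs, and the Independent Variables text treats female caseload and workload as characteristics that vary between DWHPs.

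At stake is how the power statement is read. Someone who sees a cell close to or below 80% may take the sentence as assurance of unstated slack, and may later read too much into a null result.

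**Working it through.** **Inputs.** From the plan: two-sided 5% level, 80% power, two-proportion z-test, ICC 0.03 or 0.05, m = 25 or 50 episodes per DWHP per arm, the four pairs of proportions in Table 2, and about 20 DWHPs per arm. Assumed: the CV of episode counts, shown from 0.4 to 0.8.

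**1. Reproduce Table 2.**

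Episodes per arm without clustering: n = (1.960 + 0.842)² × [p₁(1−p₁) + p₂(1−p₂)] / (p₁−p₂)². Rounded up, n is 197 (80 vs 90%), 112 (67 vs 83%), 313 (67 vs 77%) and 225 (50 vs 63%).

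DWHPs per arm: k = n × [1 + (m−1)ICC] / m. The design effects are 1.72 and 2.20 (m = 25) and 2.47 and 3.45 (m = 50). For 67 vs 77%:
- 313 × 1.72/25 = 21.5, so 22
- 313 × 2.20/25 = 27.5, so 28
- 313 × 2.47/50 = 15.5, so 16
- 313 × 3.45/50 = 21.6, so 22

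All 16 cells match in this way. With the pooled variance and n rounded up first, 14 match and the other two are 10.03 (stated 10) and 20.06 (stated 20). The table therefore gives every DWHP the same count.

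**2. Direction of the effect of unequal counts, at a fixed mean m.**

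- Every episode weighted equally: DE = 1 + [(1+CV²)m − 1]ICC. This exceeds the equal-count value by CV² × m × ICC.
- Efficient weighting in a clustered model: the equal-count DE is divided by RE = 1 − CV²λ(1−λ), where λ = m·ICC/(m·ICC + 1 − ICC). This is the usual approximation, and RE is below 1 whenever CV > 0.

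Both lower power. The second lowers it less.

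**3. Size, for 20 DWHPs per arm, m = 25, ICC 0.05.**

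At CV 0.6:
- Equal weighting: DE = 1 + (1.36 × 25 − 1) × 0.05 = 2.65.
- Efficient weighting: λ = 1.25/2.20 = 0.568; RE = 1 − 0.36 × 0.568 × 0.432 = 0.912; DE = 2.20/0.912 = 2.41.
- Effective episodes per arm: 500/2.20 = 227 with equal counts, 500/2.65 = 189 with equal weighting, 500/2.41 = 207 with efficient weighting.

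Power = Φ{(|p₁−p₂| − 1.96√[2p̄(1−p̄)/nₑ]) / √[(p₁(1−p₁) + p₂(1−p₂))/nₑ]}, where nₑ is the effective number and p̄ the mean proportion. Cells show equal / efficient weighting:

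| Effect | Equal counts | CV 0.4 | CV 0.6 | CV 0.8 |
|---|---|---|---|---|
| 50 vs 63% | 80.0% | 76.5 / 78.4% | 72.3 / 76.3% | 66.9 / 73.0% |
| 80 vs 90% | 85.0% | 81.8 / 83.5% | 77.9 / 81.6% | 72.7 / 78.5% |
| 67 vs 83% | 97.8% | 96.7 / 97.3% | 95.1 / 96.7% | 92.5 / 95.4% |

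At CV 0.6, efficient weighting recovers about half of the loss: for 50 vs 63%, the loss is 3.7 points instead of 7.7.

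**4. A separate result, with equal counts.** For 67 vs 77% at 20 DWHPs per arm:

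| m | ICC | Effective episodes per arm | Power |
|---|---|---|---|
| 25 | 0.03 | 500/1.72 = 291 | 76.7% |
| 25 | 0.05 | 500/2.20 = 227 | 66.2% |
| 50 | 0.03 | 1000/2.47 = 405 | 88.8% |
| 50 | 0.05 | 1000/3.45 = 290 | 76.6% |

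Three of the four are below 80%. Table 2 shows the same thing, since it asks for 22, 28 and 22 DWHPs in those cells.

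**5. Features of the design that Table 2 leaves out (67 vs 77%, 20 DWHPs).**

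- *Gain.* Suppose the same DWHPs serve in both periods, the between-period correlation is half the within-period one (assumed), and there is no period adjustment. Then DE = 1 + [(1+CV²)m × 0.5 − 1]ICC. With m = 25 and CV 0.6 this is 1 + 16 × 0.03 = 1.48 (power 82.7%) or 1 + 16 × 0.05 = 1.80 (74.8%), against 76.7% and 66.2% in step 4.
- *Cost.* A generalised least-squares calculation with period effects and a DWHP random effect, one system per step, equal counts and 2 to 5 systems (assumed; the documents give no number) gives about 44 to 62% with 50 episodes per DWHP in total, and about 71 to 86% with 100. Clustering by healthcare system is not included in these figures.

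**The case against.** **The adjustment helps.** A reader might infer that adjusting for episode counts itself costs power, or recovers nothing. Neither is right. The unequal counts cost power, and an efficiently weighted clustered analysis reduces the cost. The equal-weighting figures are therefore the upper end of the loss. This stands, and it is why both figures are shown. It still does not turn unequal counts into a gain.

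**Covariates are the other ground.** They may add precision. The documents give no figure for it, so this ground is possible but not demonstrated.

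**The CV is not known.** The text on classifying guideline-adherent care speaks of a sample of episodes, so sampling could even out the counts. No quota is stated. At a CV of 0.4 the loss is modest: 1.6 to 3.5 points for 50 vs 63% in the table above.

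**Table 2 may be conservative for another reason.** It treats the arms as independent, although each healthcare system contributes to both periods. Step 5 shows that this could outweigh the effect of unequal counts. It also shows that period adjustment can outweigh the gain. So a reader who infers that Table 2 as a whole is too optimistic goes further than the documents allow.

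**The power claim has its own basis.** A reader might also infer that the claim of more than 80% power depends on the conservative sentence. It does not: it rests on Table 2 and on about 20 DWHPs per arm. Its failure for 67 vs 77% is a separate matter, present with equal counts.

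**Conclusion.** The point holds in a limited form. Table 2 contains no arithmetic error. What is unsupported is the property claimed for it. The episode-count ground points towards less power, the covariate ground is unquantified, and the net effect of the features that Table 2 omits is not settled.

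The size depends on a CV that the documents do not give. At an assumed CV of 0.6, with 20 DWHPs per arm, 25 episodes and ICC 0.05, the loss is about 4 to 8 points for 50 vs 63% and 3 to 7 points for 80 vs 90%. This takes the first below 80% under either weighting, and the second below 80% only if every episode is weighted equally. Power for 67 vs 83% stays above 95%, so not every scenario is at risk.

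Independently of any CV, the statement of more than 80% power does not hold for 67 vs 77% at 20 DWHPs in three of the four combinations of episode count and ICC.

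**What to change.** 1. Delete the sentence that calls the calculations conservative.
2. Estimate the CV of episodes per DWHP from the baseline records, which the footnote to Table 1 says are assessed retrospectively. If episodes will be sampled to a set number per DWHP, state that number.
3. Recompute Table 2 with unequal counts under the planned clustered stepped-wedge model. State the number of systems and steps, whether the same DWHPs serve in both periods, and what is assumed about clustering by system. Report 1 + [(1+CV²)m − 1]ICC as the equal-weighting bound.
4. Restate the power, or the smallest detectable difference, for about 20 DWHPs, and limit the claim of more than 80% power to the effects for which it holds. Any credit taken for covariates should be given as a figure with its source.

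This needs a recalculation and new wording. No added DWHPs are required. The cost is a stated power that is likely to be less favourable.

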We hypothesize that *DWHP Support* will improve the quality and efficiency of WH care in CBOCs. We expect that these effects may be influenced by baseline characteristics of the DWHPs (e.g., time in practice), patient conditions and characteristics, and practice characteristics, as well as DWHPs' use of the intervention. For this aim, our analytic sample will be limited to sites participating in DWHP Support outside of GLA, given that DWHP support was piloted in GLA and therefore does not have a recent "control" period (i.e., GLA was contaminated by the pilot). We will, however, use GLA data to pilot our electronic medical record (EMR) data abstraction procedures. We will also collect GLA e-consult data because this data were not contaminated by the piloting of SCAN-ECHO at GLA.

Dependent Variables: The main outcome measures will be quality of care defined by adherence to practice guidelines. We will assess quality of care and efficiency of care using the VA electronic medical records (EMR) of all female patients seen by DWHPs during the data collection period. With the modified stepped wedge design, each participating site healthcare system is contributing data to both intervention and control periods, thereby addressing comparability concerns. We expect to identify multiple episodes of care per DWHP over the combined data collection periods, where we define an episode of care as the care initiated by the DWHP for a WH condition, irrespective of whether it occurs over one or multiple encounters, and is face-to-face or not.⁵⁴

Electronic medical record (EMR) data abstraction: To assemble the relevant data from the EMR using the VHA Health Information Access (HIA) program's Data Use Agreement protocols, we will use the *Corporate Data Warehouse (CDW)*, accessed through VINCI and discussed above and, as needed, the Compensation and

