% of episodes of care with fully proficient care quality and efficiency Control Intervention (effect size)		25 episodes per DWHPper study arm* ICC=0.03 ICC=0.05		50 episodes per DWHPper study arm* ICC=0.03 ICC=0.05	
80%	90% (medium)	14	18	10	14
67%	83% (medium)	8	10	6	8
67%	77% (small)	22	28	16	22
50%	63% (very small)	16	20	12	16

^{*}study arm refers to intervention versus control, and includes all data collection

Aim #2:

We hypothesize that *DWHP Support* will increase DWHPs' practice expertise, and thereby modify their practice behavior, resulting in improved quality and efficiency (the focus of Aim 1). To test this hypothesis, we will collect process outcomes for the components of the intervention and their effects on patient care with a SCAN/e-consult referring provider survey (here after referred to as e-consult survey).

Provider Behavior: e-consult referring DWHP brief surveys: We will obtain the names of participating providers who initiate gynecology e-consults by obtaining from CDW, through VINCI, a list of all participating site gynecology e-consults. After each e-consult has been completed, we will email a request for the providers who initiated the consult to complete a brief survey about the encounter, including if and how it impacted their management plan. More specifically, we will ask: to what extent the consult altered the diagnostic, patient counseling, and/or treatment plans for this patient; the provider's confidence in their ability to implement the recommended diagnostic, patient counseling and/or treatment plans; how much, if at all, the provider learned something from the consult; and how, if at all, the consult affected the provider's plans to refer the patient for an in-person consultation. For the referring provider surveys, we will use the question about effect on the provider's plans to refer the patient to separately estimate number of avoidable consults averted by the availability of e-consults. An open-ended question, asking for additional comments, will also be included. The e-consult referring provider survey will be administered online (using Inquisite software) and responses will be confidential.

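### The unqualified claim of more than 80% power at about 20 DWHPs per arm conflicts with Table 2 for 67% vs 77%: materially in one cell (28 needed), marginally in two (22 needed)

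*Combined protocol and SAP*

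**What the plan says.** The power section under Specific Aim #1 treats the episode of care as the unit of analysis, clustered within DWHP, with ICC values of 0.03 and 0.05. Of 0.05 it says: "The latter is relatively large compared to results that have been reported in the literature". The test and target are stated as: "The calculations assume a two-tailed 5% significance level and power of 80% to detect a difference between the study arms". The test is a simple z-test for two proportions. Because the real analysis will use covariates and the actual episode counts, the section adds: "Thus, it can be assumed that the sample size calculations presented here are conservative". No figure supports that remark.

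The next paragraph takes a 67% baseline from preliminary data. With 25 episodes per DWHP it claims small to medium effects are detectable. With 50 episodes, "then with a baseline proficiency of 67%, we could detect a small intervention effect". It closes with: "The number of available DWHPs (approximately 20 per study arm) and episodes of care provides us with >80% power".

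The table that follows is headed "Table 2: Number of DWHPs needed to detect the effects in each scenario with 80% power". Its row for a 67% control rate reads "77% (small) 22 28 16 22", in the order 25 episodes (ICC 0.03, 0.05), then 50 episodes (ICC 0.03, 0.05).

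**The concern.** Three of the four entries in the 67% vs 77% row exceed 20, one of them by 40% (28 against 20). The closing sentence attaches no scenario to its claim, so it reads as covering the whole table.

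The row is an important one. The 67% baseline is the only one drawn from the plan's own data; 80% and 50% are introduced as alternatives. Of the two effects tabulated at 67%, this is the smaller, and the text says it can be detected. A reader who relies on the sentence after a null result would credit the trial with more ability to pick up a 10-point improvement than the plan's calculation supports, above all at 25 episodes per DWHP.

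**Working it through.** **Inputs** (all from the power section and Table 2): two-sided alpha 0.05 (z = 1.960); power 80% (z = 0.842); ICC ρ = 0.03 or 0.05; m = 25 or 50 episodes per DWHP; p1 = 0.67, p2 = 0.77; K = 20 DWHPs per arm. Equal arms are assumed.

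**Step 1: reproduce Table 2.**

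Episodes per arm before clustering, unpooled: n = (1.960 + 0.842)² × [p1(1−p1) + p2(1−p2)] / (p2−p1)².

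DWHPs per arm: n × [1 + (m−1)ρ] / m, rounded up.

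Design effects: 1 + 24×0.03 = 1.72; 1 + 24×0.05 = 2.20; 1 + 49×0.03 = 2.47; 1 + 49×0.05 = 3.45.

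| Control vs intervention | n | DWHPs per arm, in column order | Printed |
|---|---|---|---|
| 80% vs 90% | 196.2 | 14, 18, 10, 14 | 14, 18, 10, 14 |
| 67% vs 83% | 111.0 | 8, 10, 6, 8 | 8, 10, 6, 8 |
| 67% vs 77% | 312.5 | 22, 28, 16, 22 | 22, 28, 16, 22 |
| 50% vs 63% | 224.4 | 16, 20, 12, 16 | 16, 20, 12, 16 |

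All 16 cells match as per-arm counts. They cannot be totals over both arms, because this row would then read 44, 56, 32, 44. A pooled-variance test gives n = 315.3 for the row and the same four counts (21.7, 27.7, 15.6, 21.8 before rounding). Over the whole table the pooled version matches 15 of 16 cells; the exception is 10.01 against a printed 10.

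**Step 2: power for 67% vs 77%.** With effective episodes per arm n_e = K×m / [1 + (m−1)ρ] and p̄ = 0.72:

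power = Φ{ [0.10√n_e − 1.960√(2p̄(1−p̄))] / √(p1(1−p1) + p2(1−p2)) }

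| m, ICC | n_e at K = 20 | K = 18 | K = 20 | K = 22 |
|---|---|---|---|---|
| 25, 0.03 | 290.7 | 72.3% | **76.7%** | 80.6% |
| 25, 0.05 | 227.3 | 61.6% | **66.2%** | 70.3% |
| 50, 0.03 | 404.9 | 85.4% | **88.8%** | 91.5% |
| 50, 0.05 | 289.9 | 72.2% | **76.6%** | 80.4% |

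The columns for 18 and 22 assume a range for what approximately 20 might mean. The unpooled version at 20 gives 77.1%, 66.6%, 89.0% and 77.0%, so the choice of variance hardly matters.

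**Step 3: the rest of the table.** At 20 per arm the other three rows all reach 80%. The lowest is 50% vs 63% (25 episodes, ICC 0.05) at 80.03%, which falls to 75.7% at 18. Cells met: 12 of 16 at 18, 13 at 20, 15 at 22. The one cell never met in that range is 67% vs 77% with 25 episodes and ICC 0.05.

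**Step 4: what 20 per arm does deliver.** From 67%, the difference detectable with 80% power is about 10.4, 11.7, 8.9 and 10.4 points, in column order. For a 10-point difference the break-even ICC is 0.024 at 25 episodes and 0.044 at 50. The 50-episode statement therefore holds at ICC 0.03 but not at 0.05.

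**Step 5: how much the conservative margin would have to be worth.** Variance reduction needed for 80% at 20 per arm: 1 − 20/21.69 = 7.8%; 1 − 20/27.75 = 27.9%; 1 − 20/21.76 = 8.1%. In the 28-DWHP cell it is still 1 − 22/27.75 = 20.7% at 22 per arm.

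**The case against.** The strongest defence has four parts.

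- **Approximately 20 may include 22.** This stands for the two 22-DWHP cells, which is why they are called marginal. It does not help the 28-DWHP cell. The word also allows fewer than 20, and at 18 a fourth cell fails.
- **The sentence closes a paragraph that refers to Table 2, claims only small to medium effects at 25 episodes, and fixes no episode yield.** In part this stands. The detectable differences of 10.4 and 11.7 points at 25 episodes lie between the table's small effect (10 points) and medium effect (16 points), so that wording is acceptable. Higher yields would also help: 80% power at 20 per arm needs about 30 episodes per DWHP at ICC 0.03 and about 71 at ICC 0.05. But the plan's scenarios are 25 and 50, and the closing sentence claims more than the paragraph does.
- **ICC 0.05 is described as relatively large.** True, but it is one of the plan's two planning values. At 25 episodes, 20 DWHPs also fall short at 0.03, though only slightly.
- **The z-test is a simplification, and the design compares periods within the same systems.** The Dependent Variables text says "each participating site healthcare system is contributing data to both intervention and control periods", and the independent-arm formula gives no credit for this. As an illustration only, suppose the correlation between periods within a DWHP is half the ICC and there is no calendar-time adjustment. The design effect in the worst cell becomes 2.20 − 25×0.025 = 1.575, a 28% reduction, which brings power to about 80%. The plan states no such correlation, however, and adjusting for calendar time in a non-randomised rollout would take back some of the gain. Actual power could be higher or lower.

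It is also fair to say that a confidence interval, not planned power, decides what a null result excludes, and that the requirements are printed just below the sentence. Both points limit the harm. Neither makes the sentence agree with the table.

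**Conclusion.** The concern holds. As written, the statement of more than 80% power is contradicted by the plan's own Table 2 for 67% vs 77%. At 20 DWHPs per arm the plan's method gives 66% to 89% power for that row, depending on episode yield and ICC. One cell is about 14 points short (80 − 66.2 = 13.8) and stays short at 22 per arm. Two are about 3.3 points short and recover at 22. The statement is correct for the other 13 cells, in one of them only just.

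These figures rest on equal arms, the independent-arm z-test and the single-level design effect, which are the assumptions that reproduce Table 2. They are not the power of the stepped-wedge analysis, which the plan does not calculate. The plan should correct the sentence; the design does not have to change on this account.

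**What to change.** Replace the closing sentence with one tied to the scenarios, for example:

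> Under the simplified independent-arm z-test, 20 DWHPs per study arm gives at least 80% power for every Table 2 scenario except 67% vs 77% with 25 episodes per DWHP (about 77% at ICC 0.03 and 66% at ICC 0.05) and with 50 episodes at ICC 0.05 (about 77%). From a 67% baseline, the difference detectable with 80% power is about 10.4 points (25 episodes, ICC 0.03), 11.7 (25, 0.05), 8.9 (50, 0.03) and 10.4 (50, 0.05). These approximations do not model the stepped-wedge analysis.

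Among the tabulated scenarios, tie the 50-episode small-effect statement to ICC 0.03. The small-to-medium wording for 25 episodes can stay.

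The cost is wording only: no added enrolment and no change to the endpoint, test or conduct. The stated power becomes slightly less favourable.

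### Table 2 sizes the DWHP groups with normal quantiles; under its own independent-arm model a small-sample correction adds one DWHP per arm to each cell, and the Aim 1 test needs a stated small-sample reference.

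*Combined protocol and SAP*

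**What the plan says.** The Sample Size and Power Calculations section states: "The calculations assume a two-tailed 5% significance level and power of 80% to detect a difference between the study arms". The sizing method is also stated: "The statistical test involved is a simple z-test for the comparison of two proportions". On clustering: "We will assume two values for the intra-cluster correlation coefficient (ICC): 0.03 and 0.05", and "we performed the calculations via the single level of clustering within DWHPs, with the episode of care as the unit of analysis". Correlation between DWHPs is taken as little or none, so under this model the DWHP is the independent unit.

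The results stand under the title "Table 2: Number of DWHPs needed to detect the effects in each scenario with 80% power". Table 2 has columns for 25 and for 50 episodes ("25 episodes per DWHPper study arm* ICC=0.03 ICC=0.05" heads the first pair). Its entries run from 6 to 28. Two of its rows read "90% (medium) 14 18 10 14" and "83% (medium) 8 10 6 8".

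The text puts availability at about 20 DWHPs per arm, says that this gives more than 80% power, and calls the calculations conservative because the real analysis will be more elaborate. The Aim #1 Statistical Analysis section names a generalized linear model with a logit link. Neither section mentions a t reference, degrees of freedom or any other small-sample adjustment, for the sizing or for the analysis.

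**The concern.** A normal quantile is exact only when the variance in the denominator is known. In a clustered comparison, the part that matters most is the variance between DWHPs, and the data on it come from the DWHPs themselves: as few as 6 per arm in Table 2. Something then has to give. If the final test uses a t reference, power at the printed counts is below the stated 80%. If it keeps the 1.96 cut-off, the level is above the stated 5%. The plan does not say which reference it will use, so either property could be lost unnoticed, and the word conservative points the wrong way on this item.

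**Working it through.** **Inputs** (Sample Size and Power Calculations; Table 2): two-sided 5%, power 80%; rates 80/90, 67/83, 67/77 and 50/63; m = 25 or 50 episodes per DWHP per arm; ICC 0.03 or 0.05; about 20 DWHPs available per arm.

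**Step 1: reproduce Table 2.** DWHPs per arm = (1.960 + 0.842)² × [p1(1−p1) + p2(1−p2)] / (p1−p2)² × [1 + (m−1)ICC] / m.

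- Example, 67% vs 83%, m = 50, ICC 0.03: 7.849 × (0.2211 + 0.1411) / 0.0256 = 111.0 episodes per arm. The design effect is 1 + 49 × 0.03 = 2.47. Then 111.0 × 2.47 / 50 = 5.49, rounded up to 6. Table 2 prints 6.
- Rounding up gives the printed figure in all 16 cells. The pooled-variance form agrees too, except that one cell comes to 10.01 and is printed as 10.

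So the entries are per-arm counts from normal quantiles.

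**Step 2: replace the normal by t.** SE = √{[p1(1−p1) + p2(1−p2)] × [1 + (m−1)ICC] / (mn)}. Power comes from the noncentral t with 2n−2 degrees of freedom and noncentrality |p1−p2| / SE.

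- Same example, n = 6: SE = √(0.3622 × 2.47 / 300) = 0.0546; noncentrality 0.16 / 0.0546 = 2.93; critical value on 10 df 2.228; power 75.2%. At n = 7 it is 82.7%.

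Power at the printed count (count in brackets):

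| Rates | m=25, ICC 0.03 | m=25, ICC 0.05 | m=50, ICC 0.03 | m=50, ICC 0.05 |
|---|---|---|---|---|
| 80/90 | 78.4% (14) | 79.4% (18) | 76.8% (10) | 78.3% (14) |
| 67/83 | 76.0% (8) | 76.4% (10) | 75.2% (6) | 75.9% (8) |
| 67/77 | 79.1% (22) | 79.3% (28) | 78.8% (16) | 78.9% (22) |
| 50/63 | 78.8% (16) | 78.5% (20) | 79.6% (12) | 78.7% (16) |

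The five cells more than 2 points short all have 10 or fewer DWHPs per arm. The smallest n that reaches 80% is the printed entry plus one in every cell.

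**Step 3: level if 1.96 is kept.** Level = 2 × P(t > 1.96) on 2n−2 df: 7.8% at n = 6, 7.0% at 8, 6.6% at 10, 5.7% at 20, 5.5% at 28. A beta-binomial simulation of the same model agrees: with the t-test, level 4.9% to 5.1% and power 75.1% to 79.7%; with the 1.96 cut-off, level 5.5% to 7.8%.

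**Step 4: at about 20 per arm.** For 50% vs 63%, m = 25, ICC 0.05, power goes from 80.5% (normal, same variance form) to 78.5% (t). No other cell crosses 80% because of the correction. The 80/90 row has 83.6% to 97.5% and the 67/83 row 97.4% to 99.9%, both with t. In the 67/77 row, three cells are short already, because Table 2 itself asks for 22, 28 and 22. That is a separate matter.

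**Step 5: same DWHPs in both periods.** Let c be the correlation of a DWHP's effect between periods. The variance of the difference is {[v1 + v2] × [1 + (m−1)ICC] / m − 2c × ICC × √(v1v2)} / n, with v = p(1−p), on n−1 df and with no period effects. The plan gives no c, so these values are assumptions:

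| Assumed c | Power at printed counts | Cells below 80% |
|---|---|---|
| 0 | 65% to 78% | 16 |
| 0.2 | 71% to 83% | 7 |
| 0.5 | 79% to 92% | 2 |
| 0.8 | 86% to 99% | 0 |

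Keeping 1.96 with 20 DWHPs in both periods (19 df) gives a level of 6.5%.

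**The case against.** The strongest reply is that Table 2 is coherent on its stated terms. A z-test that takes the ICC as known holds a level of about 5% and power of 80% to 83% at these counts. No figure is miscalculated. That stands: this is a matter of approximation, not an arithmetic slip. It does not settle the point, because the plan nowhere says that the analysis will fix the ICC in advance.

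The second reply is that 2n−2 degrees of freedom assume two separate groups of DWHPs. The Dependent Variables text under Specific Aim #1 has each healthcare system supplying both control and intervention data, and the sizing section defines the arms as periods. This also stands, and it limits the claim. A reader might infer that no Table 2 cell can deliver both 5% and 80% in this trial. The documents do not support that: Step 5 shows power on either side of 80%, depending on a correlation that is not given. Nor does pairing vindicate the printed counts, since the calculation takes no credit for it.

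The third reply is materiality: the largest losses fall where 6 to 10 DWHPs are needed and about 20 are available. That is correct.

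Finally, silence on the reference distribution is not a commitment to 1.96. True, so the level figures describe what would follow from a normal reference, not what the plan has said it will do.

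**Conclusion.** The point holds in a limited form and is minor. Under Table 2's own model, with the between-DWHP variance estimated, the printed counts give 75.2% to 79.6% power and each is one DWHP per arm short. At about 20 per arm the correction alone changes the reading of one cell, and since availability is itself approximate, 20 against 21 should not be pressed.

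A reader might also conclude that the trial is materially underpowered for this reason. The documents do not support that: the loss is at most 4.8 points (80 − 75.2), and it falls in cells with a large surplus of DWHPs. Non-randomised steps, period effects and clustering by healthcare system could cost further power, but the plan gives no number of steps or systems from which to quantify that.

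What holds under either reading of the design is the need for a stated reference. A normal one at about 20 DWHPs gives a level of about 5.7% with independent arms and 6.5% if the same DWHPs serve in both periods.

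**What to change.** 1. In Aim #1 Statistical Analysis, state that the intervention test uses a small-sample reference (t, or a bias-reduced variance estimate) with degrees of freedom based on the number of DWHPs.
2. Restate Table 2 with t quantiles. By row: 15, 19, 11, 15; 9, 11, 7, 9; 23, 29, 17, 23; 17, 21, 13, 17.
3. Label the table as an approximation for two independent arms, and say whether the same DWHPs are expected to contribute to both periods. If so, show power over a range of between-period correlations.
4. Do not describe the calculation as conservative on this point.

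The cost is a recalculation and a few sentences. The stated figures become slightly less favourable; data collection does not change.
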